4.3.1. Arm A (Monotherapy) - Safety Evaluation

Approximately 3-6 HR MDS subjects will receive GSK2879552 2 mg once daily to evaluate the safety and tolerability of GSK2879552. If the number of subjects with DLT is 0 (out of 3) or ≤ 1 (out of 6), RP2D for MDS will be considered defined. Subjects who fail to take at least 75% of their scheduled doses in the 4 weeks for reasons other than toxicity will be replaced.

If the 2 mg daily dose is not well tolerated, a reduced dose will be evaluated to determine RP2D for monotherapy in HR MDS. Part 2 enrolment will begin when the RP2D is confirmed in both mono therapy and combination arm. See Section 4.10 for dose justification.

4.3.2. Arm B (Combination) - Dose Escalation

Using the 3 + 3 procedure, up to six subjects will be enrolled at each dose level. Evaluation of a cohort of at least three subjects completing one cycle of treatment (defined as first 28 days) is required prior to opening the next dose level. Subjects who fail to take at least 75% of their scheduled doses in the 4 weeks for reasons other than toxicity will be replaced.

Dose escalation will progress as described in Table 1. Dose escalation decisions will take into account all available data, including the safety profile of prior cohorts.

Table 1 3 + 3 Dose Escalation Procedure

| Number of Subjects with DLT | Action |
|-----------------------------|--|
| 0 out of 3 subjects | Escalate to next dose level |
| 1 out of 3 subjects | Accrue three additional evaluable subjects at current dose level for a total of six evaluable subjects |
| 1 out of 6 subjects | Escalate to the next dose level |
| 2 or more out of 6 subjects | Maximum tolerated dose has been exceeded. Either evaluate an intermediate dose lower than current dose or expand a prior cohort up to 12 subjects. |

Two dose levels for GSK2879552 are planned to be explored with a fixed dose of azacitidine (Table 2). In addition, alternate dose levels and schedules may also be explored based on emerging toxicity and PK data. The dose escalation will complete when emerging DLTs prohibit further escalation, or when pre-specified RP2D is reached. The RP2D will not exceed the MTD and may be chosen based on both PK and safety data.

In Part 1 Arm B, to facilitate dose escalation/de-escalation decisions, a Bayesian logistic regression model (BLRM) may be utilized to predict the probability of DLT at the dose levels yet to be tested. Specifically, a BLRM for combination treatment will be fitted on the dose limiting toxicity data (i.e., absence or presence of DLT) accumulated throughout

the dose-escalation to model the dose-toxicity relationship of GSK2879552 and azacitidine when given in combination.

Table 2 Planned Dose Levels

| Dose Level | GSK2879552 ^a | Azacitidine ^b |
|--|-------------------------|----------------------------|
| -1 | 0.5 mg once daily | 75mg/m ² |
| 1 | 1 mg once daily | 75 mg/m² |
| 2 | 2 mg once daily | 75 mg/m ² |
| a. Continuous daily dosing | | |
| b. Days 1-7 of 28 days cycle via IV or SC administration | | |

4.3.3. Dose Limiting Toxicities

An event will be considered a DLT if it occurs within the first 28 days of treatment, and meets one of the following criteria unless it can be clearly established that the event is unrelated to treatment. Subjects unable to receive at least 75% of scheduled doses (of both agents, at the intended strength) for reasons other than toxicity (e.g., acute illness, disease progression) will not be evaluable for DLT purposes:

- Grade 4 thrombocytopenia associated with clinically significant bleeding
- Any Grade 3 or greater non-hematologic toxicity
- Fatigue, asthenia, nausea, vomiting or new electrolyte disturbance that respond to standard medical care within 72 hours are exceptions
- Any toxicity considered drug related that in the judgment of the investigator and GSK Medical Monitor is dose-limiting
- Drug related toxicities that prevent subjects from taking $\geq 75\%$ of the intended doses during the first 28 days of treatment
- Treatment delay of 14 days or greater due to unresolved drug-related toxicity

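### As written, the 75% dosing rule has no exception for a subject who has had a DLT, so an observed DLT can drop out of the Part 1 count and the subject be replaced

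*Protocol*

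**What the plan says.** Protocol Section 4.3.3 defines a DLT by the event: "An event will be considered a DLT if it occurs within the first 28 days of treatment", provided that it meets a listed criterion. Doses received play no part in that definition.

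The same section then fixes who is counted. The rule opens "Subjects unable to receive at least 75% of scheduled doses (of both agents, at the intended strength") and ends "for reasons other than toxicity (e.g., acute illness, disease progression) will not be evaluable for DLT purposes". Section 4.3.1 (Arm A) adds: "Subjects who fail to take at least 75% of their scheduled doses in the 4 weeks for reasons other than toxicity will be replaced". Section 4.3.2 (Arm B) repeats that sentence.

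The DLT list contains one criterion tied to low dosing, which begins "Drug related toxicities that prevent subjects from taking". It covers doses missed because of drug-related toxicity and nothing else.

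The counts drive the decisions. In Table 1, one DLT in three subjects leads to "Accrue three additional evaluable subjects at current dose level for a total of six evaluable subjects", and two or more in six means that the MTD has been exceeded. In Arm A the RP2D is considered defined at 0 of 3 or at most 1 of 6. Section 9.3.2 makes the Section 4.3 rules the primary consideration for escalation and de-escalation.

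**The concern.** Evaluability depends on two things only: the share of doses received and the reason for any shortfall. Whether the subject has already had a DLT does not enter. A subject with a qualifying event who is below 75% because of illness or progression is therefore, read literally, removed from numerator and denominator and replaced.

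Cohorts hold three to six subjects, so one removed DLT can change the action taken, and the dose carried into Part 2 rests on this count. The rule's own examples, acute illness and progression, are foreseeable in this population: Section 2.1.2 gives a median survival after azacitidine or decitabine failure of 5.6 and 4.3 months.

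**Working it through.** The protocol states no operating characteristic or target DLT rate for Part 1 (Section 9.2.1 says that its size is not statistically driven), so there is no figure to reproduce. The results below follow from Table 1. The true DLT rate p and the loss rates d and m are assumptions.

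**Step 1: which DLTs are exposed.** Section 4.3.3 counts doses at the intended strength, and 75% of 28 daily GSK2879552 doses is 21. Table 3 in Section 5.5.2 has drug-related Grade 3-4 non-hematologic toxicity lead to a hold and then a reduction.
- If GSK2879552 is held and reduced for such a DLT by about day 20, at most 20/28 = 71% of doses are at full strength. The cause is toxicity, so the exclusion does not apply.
- From about day 21, with no earlier missed doses, 21/28 = 75% has been received and the subject is evaluable whatever follows.

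These cases remain exposed:
- An Arm B subject misses two of seven azacitidine doses through acute illness (5/7 = 71%) and then has a DLT. This takes the threshold as applying to each agent. If doses were pooled, 33/35 = 94% would pass and this example would fall away.
- Grade 4 thrombocytopenia with bleeding is followed by progression. Section 5.5.3 adjusts hematologic doses by cycle, so a within-cycle hold is not prescribed.
- Doses are missed for mixed reasons, or only azacitidine is held under the and/or wording of Table 3.

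**Step 2: one DLT in the first three subjects.**
- Counted: three more subjects are added, and escalation needs no DLT among them. P = (1-p)^3.
- Dropped: the cohort is 0 of 2 plus a replacement. If the replacement has no DLT, escalate; if there is one, the cohort is at 1 of 3 and needs 0 of 3 more. P = (1-p) + p(1-p)^3.

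| True p | Counted | Dropped and replaced |
|---|---|---|
| 0.2 | 0.512 | 0.902 |
| 0.3 | 0.343 | 0.803 |
| 0.4 | 0.216 | 0.686 |
| 0.5 | 0.125 | 0.563 |

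At p = 0.3: 0.7^3 = 0.343, and 0.7 + 0.3 × 0.343 = 0.803.

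**Step 3: two DLTs in six.** Dropping one gives 1 of 5 plus a replacement, and escalation then has probability 1-p: 0.70 at p = 0.3 and 0.60 at p = 0.4. If both are counted, the MTD has been exceeded.

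**Step 4: the rate among evaluable subjects.** Let d be the chance of falling below 75% for non-toxicity reasons in a subject with a DLT, and m the same chance in a subject without one.
- As written: r = p(1-d) / [p(1-d) + (1-p)(1-m)].
- If a DLT always counts: r = p / [p + (1-p)(1-m)].
- P(escalate) = (1-r)^3 + 3r(1-r)^2 × (1-r)^3.

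At p = 0.3 and m = 10%:

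| Rule | d | Evaluable DLT rate | P(escalate) |
|---|---|---|---|
| As written | 10% | 0.27/0.90 = 0.300 | 0.494 |
| As written | 20% | 0.24/0.87 = 0.276 | 0.545 |
| As written | 30% | 0.21/0.84 = 0.250 | 0.600 |
| DLT always counts | any | 0.30/0.93 = 0.323 | 0.449 |

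With d = m, the rate as written equals p. It falls below p only when d exceeds m.

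**The case against.** The strongest reply has three parts.

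**Other rules cover much of the gap.** A reader might take a Grade 3 non-hematologic DLT on day 8, followed by progression on day 15, as the typical lost case. The documents do not support that: the hold-and-reduce rule, the intended-strength wording and the criterion on doses prevented by toxicity generally keep such a subject in. This stands, and it confines the gap to the cases listed in the working.

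**The event is not hidden.** Section 4.3.2 has escalation decisions take all available data into account, and Section 4.3.4 has the data review team examine adverse events, including those that are not DLTs. This also stands, and it makes an unnoticed escalation unlikely. But neither provision returns the subject to the count. In Arm A the rule that begins "If the number of subjects with DLT is 0 (out of 3") treats the RP2D as defined on the count alone. The sentence on all available data stands in the Arm B section, and Section 4.3.4 concerns dose escalation.

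**The rate need not be biased.** A reader might infer that the rule necessarily understates toxicity. It does not: illness and progression also remove subjects without a DLT, and with equal loss in both groups the evaluable rate stays at p.

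One might add that any sensible team would count the DLT anyway. Doing so would depart from the written evaluability and replacement rules, and the choice would be made in an open-label study after the DLT is known.

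**Conclusion.** The gap is real and narrow. Sections 4.3.1 to 4.3.3, followed literally, can discard an observed DLT and replace the subject when the dosing shortfall has a non-toxicity cause. DLTs that themselves cause the shortfall are already protected.

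When it happens to one DLT in the first three subjects, the effect on the decision is large: the chance of escalating goes from 0.343 to 0.803 at a true rate of 0.3. It would be wrong to read this as 1 of 3 becoming 0 of 3 outright, because the replacement may also have a DLT.

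How often it would happen cannot be said from the protocol. Systematic understatement needs non-toxicity loss to be more common after a DLT, which is an assumption. The result as written, 0.494 to 0.600 at p = 0.3, holds only for the loss rates shown. The point merits a wording correction and does not call the Part 1 design into question.

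**What to change.** State in identical words in Sections 4.3.1, 4.3.2 and 4.3.3 that any subject with a DLT in the first 28 days is DLT-evaluable whatever doses were received, and that the 75% rule and replacement apply only to subjects without a DLT. It would help to say in the same sentence whether the 75% applies to each agent separately.

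The cost is one sentence in three places. No DLT criterion, dose or treatment rule changes, and fewer subjects are replaced. There is a small statistical price: when subjects without a DLT are lost, the evaluable DLT rate is slightly conservative (0.323 for a true 0.3 with 10% loss), which lowers the chance of escalating from 0.494 to 0.449 when loss is equal in both groups.

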4.3.4. Dose Escalation Committee

A data review team, consisting (at a minimum) of the investigator(s), GSK medical monitor, clinical pharmacologist, clinical scientist, and statistician, will be responsible for determining whether dose escalation during Part 1 should continue as planned according to the 3+3 design rules together with the predicted DLT rates at all dose levels under a Bayesian logistic regression model (BLRM). Prior to the dose escalation decision, the data review team will review all available data on adverse events including non-DLT toxicities, laboratory assessments and other safety evaluations.

4.4. Part 2

Part 2 of the study will be started once the dose escalation has been completed for both arms (A and B), and a dose has been selected for GSK2879552 monotherapy and combination of azacitidine with GSK2879552. Once deemed eligible, subjects will be randomly assigned at study entry to Arm A or Arm B in accordance with the randomization schedule generated by Clinical Statistics, prior to the start of the study, using validated internal software.

4.5. Intra-subject Dose-Escalation

Intra-subject dose escalations may be considered on a case-by-case basis, provided that the subject has not experienced a DLT, and a higher dose level cohort has been cleared.

Decision on intra-subject dose escalation will be made after review of all safety data and approval by a GSK Medical Monitor and discussion with the investigator.

Subjects approved for intra-subject dose escalation may require additional limited PK sampling at the higher dose as determined by GSK Clinical Pharmacology.

4.6. Intra-subject Monotherapy to Combination Arm Crossover

Subjects on monotherapy (Arm A) will be allowed to cross over (to Arm B) to be treated with the combination at RP2D at the time of progression. The crossover is allowed if a patient has not experienced intolerable toxicity on mono therapy, and has experienced disease progression (including AML) according to 2006 IWG criteria. In each case, approval for crossover has to be granted by GSK Medical Monitor.

The study site is required to provide the safety and disease assessment data of the subject, and the completed crossover form (Refer to Study Procedure Manual) at least 48 hrs prior to the crossover. The medical monitor will review the data and provide the approval for crossover with a signed crossover form.

The crossover to combination treatment Arm B should occur as quickly as possible and no later than within 4 weeks of disease progression. All assessments and samples required at the “crossover visit” as described in the Time and Event table (Section 7.1) must be completed at the time of crossover. The disease assessment and safety laboratory results at the time of crossover will be considered a new baseline as the subject starts combination treatment and continue on with the next visit (from the mono therapy).

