| Encephalopathy | Three (out of 18) subjects enrolled in 200858 study experienced encephalopathy. | 
Informed Consent Form is updated to include the risk of mental status change.
 
Protocol eligibility and monitoring criteria are modified:
 
 - subjects who have received prior treatment with temozolomide, dacarbazine, procarbazine or PARP inhibitors are excluded - Montreal Cognitive Assessment (MOCA) at baseline (pre-dose Day 1) and weekly for the first 4 weeks and monthly thereafter. - Subjects with baseline (pre-dose Day 1) MOCA score of ≤ 22 are excluded - Protocol stopping criteria is modified: - Dosing will be held and neurology consult will be required if a decrease of 3 points or more from baseline (pre-dose Day 1) MOCA score or any score of < 22 occurs or in case of any other indication of early encephalopathy as determined by patient history or physical exam |
| Azacitidine | | |
| Hematologic toxicity | Azacitidine causes anemia, neutropenia and thrombocytopenia. | 
Protocol specifies:
 
 - Subjects with major bleeding (e.g. recent GI hemorrhage or neurosurgery) within the past 4 weeks are excluded. - Laboratory assessments (complete blood count [CBC] and coagulation panel) are performed weekly for the first 4 weeks and monthly thereafter - Dose stopping/modification criteria based on CBC is provided. 
Signs and symptoms of bleeding or infection will be closely monitored and treated according to institutional standards during the study.
 |

| Potential Risk of Clinical Significance | Summary of Data/Rationale for Risk | Mitigation Strategy |
|--|---|---|
| Hepatotoxicity | Azacitidine is potentially hepatotoxic in patients with severe pre-existing hepatic impairment. | 
 - Subjects with elevated liver function test (LFT), history of/concurrent malignancy or current active liver or biliary disease are excluded. - LFT is monitored weekly for the first 4 weeks and monthly thereafter. - Treatment stopping criteria based on elevation in LFT is in place. |

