| Renal impairment | Renal toxicity ranging from elevated serum creatinine to renal failure and death have been reported in patients treated with intravenous azacitidine in combination with other chemotherapeutic agents for nonMDS conditions. Renal tubular acidosis has been also reported in patients treated with azacitidine and etoposide. Patients with renal impairment may be at increased risk for renal toxicity. Also, azacitidine and its metabolites are primarily excreted by the kidney. | 
 - Subjects with inadequate renal function are excluded - Chemistry panel including serum creatinine, BUN and electrolytes are monitored weekly for the first 4 weeks and monthly thereafter. - Treatment stopping criteria based on serum bicarbonate, creatinine and or BUN is provided. |
| Teratogenic effect | Azacitidine caused congenital malformations in animals and may cause fetal harm when administered to a pregnant woman. In animal studies, pre-conception treatment of male mice and rats resulted in increased embryofetal loss in mated females | 
 - Pregnancy test will be performed at screening and monthly thereafter. - Female subjects with child bearing potential must have a negative serum pregnancy test within 7 days of first dose of study treatment and agree to use effective contraception, during the study and for 7 days following the last dose of study treatment. - Lactating females will be excluded. - Male subjects with a female partner of childbearing potential must have either had a prior vasectomy or agree to use effective contraception from the administration of the first dose of study treatment until 3 months after the last dose of study treatment. |

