| Blood samples for exploratory studies (peripheral blood) ^{3, 11} | X | | | X | X | X | | Day 1 | X | X | |
| Bone marrow aspirate for exploratory studies ¹¹ | X | | | | | | | At time of disease assessment ¹⁷ | X ¹⁷ | X ¹⁵ | |
| Disease assessment | X | | | | | | | Day 1 | X | | |
| Bone marrow for disease assessment | X | | | | | | | as clinically indicated | X ¹⁸ | X ¹⁵ | |
| PGX samples (saliva sample) | X | | | | | | | | | | |
| PK blood sample (corresponding with exploratory BMA) ¹³ | | | | | | | | X ¹⁷ | X ¹⁷ | X ¹⁷ | |
| Transfusion Need Assessment ¹⁰ | X | | | | X | X | X | D1 | | | |
| Adverse Events | | Continuous | | | | | | | | | |
| Con Meds | | Continuous | | | | | | | | | |
| OS/PFS Assessment | | | | | | | | | | | X |

1. A blood sample will be collected for GSK2879552 PK analysis on D1 at pre-dose, 0.5, 1 hr, and 3 hrs post dose..An additional optional PK sample will be collected at 24 hours post Day 1 dose for GSK2879552 measurement.
2. A blood sample will be collected for GSK2879552 PK analysis on D7 at pre-dose, 0.5, 1 hr, and 3 hrs post dose.
3. Samples should be collected at pre-dose.
4. For women of child bearing potential only. Serum pregnancy test is required for screening, crossover and EOT visits. Urine pregnancy test is adequate during study visits.
5. A blood sample will be collected for GSK2879552 PK analysis on D15 at pre-dose and 0.5-1 hr post dose.
6. Height will be measured at screening only
7. These procedures do not need to be repeated on Day 1, if the screening visit was within 3 days and they were performed at screening.
8. PK blood sample for GSK2879552 should be taken pre-dose. PK sample will not be collected beyond 48 weeks.
9. On clinic days, study drug should be taken in the clinic after safety procedures including CBC and PK/PD samplings, if applicable are completed.
10. Platelet and blood transfusions to be assessed at designated visits and summarized per unit on a weekly cumulative basis
11. Collection of exploratory sample (peripheral blood and/or BMA) time points may be terminated at the sponsor's discretion
12. Safety laboratory blood samples (CBC, chemistry and coagulation panel) should be collected post dose on Day 7.
13. PK blood sample should be collected prior to dosing on biopsy days.
14. Azacitidine dosing can start on Day 1 of the next cycle after the cross over visit is completed.
15. Optional for all subjects

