|---|---------|-------------------|----------------|-----------------|----------------|----------------|---|--------------------|------------------------------|--|---|
| | | D 1 | D4 | D 7 | D 15 | D22 | | | | | |
| testing | | | | | | | | | | | |
| CBC | X | X ⁷ | | X ¹² | X | X | C2: D1, 7 ¹² , 15 and 22 C3 and after: D1 | X | X | | |
| Chemistry Panel including LFT | X | X ⁷ | | X ¹² | X | X | Day 1 | X | X | | |
| Coagulation Panel including a PTT and INR | X | | | X ¹² | x | X | Day 1 | X | X | | |
| PK Blood samples | | X ¹ | X ⁸ | X ⁵ | X ² | X ⁸ | C2: D1, 7, 15 and 22 D1 of C3-C12 ⁸ | | | | |
| Pregnancy test ⁴ | X | | | | | | Day 1 | X | X | | |
| Blood samples for exploratory studies (peripheral blood) ^{3, 11} | X | | X | X | X | | Day 1 | X | X | | |
| Bone marrow aspirate for exploratory studies ¹¹ | X | | | | | | At time of disease assessment ¹⁷ | X ¹⁷ | X ¹⁵ | | |
| Disease assessment | X | | | | | | Day 1 | X | | | |
| Bone marrow for disease assessment | X | | | | | | as clinically indicated | X ¹⁸ | X ¹⁵ | | |
| PGX samples (saliva sample) | X | | | | | | | | | | |
| PK blood sample (corresponding with exploratory BMA) ¹³ | | | | | | | X ¹⁷ | X ¹⁷ | X ¹⁷ | | |
| Transfusion Need Assessment ¹⁰ | X | | | X | X | X | D1 | | | | |
| Adverse Events | | Continuous | | | | | | | | | |
| Con Meds | | Continuous | | | | | | | | | |
| OS/PFS Assessment | | | | | | | | | | | X |

1. A blood sample will be collected for PK analysis on D1 at pre-dose, 0.5hr, 1 hr and 3 hrs post dose. .
2. A blood sample will be collected for PK analysis on D15 at pre-dose and between 0.5 to 1 hour.
3. Samples should be collected at pre-dose.
4. For women of child bearing potential only. Serum pregnancy test is required for screening, crossover and EOT visits. Urine pregnancy test is adequate during study visits.
5. A blood sample will be collected for PK analysis on D7 at pre-dose, 0.5, 1 hr, and 3 hrs post dose. .
6. Height will be measured at screening only
7. These procedures do not need to be repeated on Day 1, if the screening visit was within 3 days and they were performed at screening.
8. PK blood sample for GSK2879552 should be taken pre-dose around the same time as CBC. PK sample will not be collected beyond 48 weeks.
9. On clinic days, study drug should be taken in the clinic after safety procedures including CBC and PK/PD samplings, if applicable are completed.

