4. For women of child bearing potential only. Serum pregnancy test is required for screening and EOT visits. Urine pregnancy test is adequate during study visits.
5. A blood sample will be collected for GSK2879552 PK analysis on D15 at pre-dose and 0.5-1 hr post dose.
6. Height will be measured at screening only
7. These procedures do not need to be repeated on Day 1, if the screening visit was within 3 days and they were performed at screening.
8. PK blood sample for GSK2879552 should be taken pre-dose. PK sample will not be collected beyond 48 weeks.
9. On clinic days, study drug should be taken in the clinic after safety procedures including CBC and PK/PD samplings, if applicable are completed.
10. Platelet and blood transfusions to be assessed at designated visits and summarized per unit on a weekly cumulative basis
11. Collection of exploratory sample (peripheral blood and/or BMA) time points may be terminated at the sponsor's discretion
12. Safety laboratory blood samples (CBC, chemistry and coagulation panel) should be collected post dose on Day 7 or the last day of Azacitidine in the cycle.
13. PK corresponding blood sample should be collected prior to dosing
14. Azacitidine dosing on Mon-Fri (Days 1-5) and Mon-Tue (Days 8-9) may be allowed on a case by case.
15. Optional for all subjects
16. Subjects are followed every 2 months to collect the survival, PFS data and the start of new treatment via chart review, or phone call contact. The follow-up will continue until death, lost to follow-up, withdrawal of consent or up to 12 months from end of treatment visit, whichever occurs first.
17. The exploratory BM sample is collected whenever the bone marrow is done for disease assessment and/or at time of crossover, unless the sample collection is stopped per sponsor discretion; the PK corresponding blood sample will be collected pre-dose at the crossover visit if the exploratory BM sample is collected. The PK corresponding blood sample will not be collected if a regularly scheduled PK sample is already being collected during the visit.
18. A window of 14 days is allowed for BM exam. Subjects who progressed to AML and cross over to Arm B will be required to have bone marrow for disease assessment prior to the start of combination dosing
19. All procedures scheduled on Day 7 visit (of any cycle) should move to Day 9, if azacitidine is given on Mon-Fri (Days 1-5) and Mon-Tue (Days 8-9) instead of Days 1-7.

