Time and Events Table - Arm B (Combination with Azacitidine), Part 2

| | SC R | Cycle 1 (28 days) | | | | | Subsequent Cycles | End of Treatment Visit | Post Treatment Bi- monthly Follow-Up ¹⁶ |
|-----------------------------------|---------|--|----|------------------|------|-----|---|---------------------------|---|
| | | D 1 | D4 | D7 ¹⁸ | D 15 | D22 | | | |
| Office Visit for Arm B (combo) | X | X | X | X | X | X | C2: D1- 7 ¹⁸ , 15 and 22 C3 and after: D1-7 | X | |
| Informed consent | X | | | | | | | | |
| Demography | X | | | | | | | | |
| Medical history | X | | | | | | | | |
| Disease characteristics | X | | | | | | | | |
| GSK2879552 Dosing ⁹ | | <----- Daily or per dosing schedule -----> | | | | | | | |
| Azacitidine dosing ¹⁴ | | <--Days 1-7--> | | | | | Days 1-7 | | |
| Review subject dosing diary | | | | X | X | | Day 1 | X | |
| GSK2879552 Drug Dispensing | | X | | | | | Day 1 | | |
| Complete physical exam | X | | | | | | | X | |
| Brief physical exam | | X ⁷ | | X | | | Day 1 | | |
| Montreal Cognitive Assessment | X | X | | X | X | X | Day 1 | | |
| ECOG PS | X | X ⁷ | | X | | | Day 1 | X | |
| Vital Signs | X | X ⁷ | | X | X | | Day 1 | X | |
| Height and weight ⁶ | X | X ⁷ | | X | | | Day 1 | X | |
| ECHO/MUGA | X | | | | | | | | |
| 12-lead ECGs | X | X ⁷ | | X | | | Day 1 | X | |
| HIV, HBsAg and HCV Ab testing | X | | | | | | | | |

| | SC R | Cycle 1 (28 days) | | | | | Subsequent Cycles | End of Treatment Visit | Post Treatment Bi- monthly Follow-Up ¹⁶ |
|---|-----------------|-------------------|----------------|------------------|----------------|----------------|--|---------------------------|---|
| | | D 1 | D4 | D7 ¹⁸ | D 15 | D22 | | | |
| CBC | X | X ⁷ | | X ¹² | X | X | C2: D1, 7 ^{12, 18} , 15 and 22 C3 and after: D1 | X | |
| Chemistry Panel including LFT | X | X ⁷ | | X ¹² | X | X | Day 1 | X | |
| Coagulation Panel including a PTT and INR | X | | | X ¹² | x | X | Day 1 | X | |
| PK Blood samples | | X ¹ | X ⁸ | X ⁵ | X ² | X ⁸ | C2: D1, 7 ¹⁸ , 15 and 22 D1 of C3-C12 ⁸ | | |
| Pregnancy test⁴ | X | | | | | | Day 1 | X | |
| Blood samples for exploratory studies (peripheral blood)^{3, 11} | X | | X | X | X | | Day 1 | X | |
| Bone marrow aspirate for exploratory studies¹¹ | X | | | | | | At time of disease assessment ¹⁷ | X ¹⁵ | |
| Disease assessment | X | | | | | | Day 1 | X | |
| Bone marrow for disease assessment | X ¹⁹ | | | | | | bone marrow if clinically indicated | X ¹⁵ | |

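### On the natural reading of Section 4.6, a crossover subject whose first combination cycle is Cycle 3 or later has no scheduled safety laboratory test after Day 1 of that cycle

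*Protocol*

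**What the plan says.** **Crossover (Section 4.6).** An Arm A subject who progresses may move to the combination with the medical monitor's approval. Disease and laboratory results at crossover are "considered a new baseline as the subject starts combination treatment and continue on with the next visit (from the mono therapy"). No sentence says whether cycle numbering restarts.

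**Start of azacitidine (Section 7.1, footnote 14 of both Arm A tables).** "Azacitidine dosing can start on Day 1 of the next cycle after the cross over visit is completed".

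**Laboratory schedule (Section 7.1).** The CBC row of the Arm A and Arm B tables gives Days 1, 7, 15 and 22 in Cycle 2 and then thins out: "15 and 22 C3 and after: D1". Chemistry/LFT and coagulation are on Day 1 only in every cycle after the first.

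**Risk mitigation (Section 4.11.1, azacitidine rows).** For hematologic toxicity, CBC and coagulation "are performed weekly for the first 4 weeks and monthly thereafter". For hepatotoxicity, "LFT is monitored weekly for the first 4 weeks and monthly thereafter". For renal impairment, "Chemistry panel including serum creatinine, BUN and electrolytes are monitored weekly for the first 4 weeks and monthly thereafter".

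**The concern.** Crossover is the point at which azacitidine is first added to GSK2879552 for that subject. Section 4.10.2 notes that the two agents had never been given together in humans and that their hematologic toxicity may overlap. Section 4.6 also admits subjects who have progressed to AML. Subjects assigned to Arm B have weekly laboratory tests in their first combination cycle. A crossover subject who simply takes up the next monotherapy visit enters a part of the schedule already thinned out for people established on treatment. The weekly tests listed against azacitidine's hematologic, hepatic and renal risks are then either not scheduled while the subject first receives it on study, or depend on how each site reads one clause.

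**Working it through.** The plan states no figure to reproduce; the check is a count of scheduled test days.

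**Step 1: when the first combination cycle falls.** Section 9.3.2.1 puts disease assessments every 4 weeks, and the tables place them on Day 1 from Cycle 2. With 28-day cycles, the first scheduled on-treatment assessment is Cycle 2 Day 1, which is Day 28 + 1 = 29. If progression is found there, footnote 14 puts azacitidine at Cycle 3 Day 1, which is Day 56 + 1 = 57. A Cycle 2 start needs progression to be found, and the crossover visit completed, during Cycle 1. On the scheduled assessments, Cycle 3 or later is therefore the usual case.

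**Step 2: scheduled test days within the first combination cycle.** With continued numbering, the Arm A and Arm B tables give the same laboratory days, so it does not matter which one the site follows.

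| Panel | Arm B Cycle 1 | Crossover, first combination cycle = C2 | Crossover, first combination cycle = C3 or later |
|---|---|---|---|
| CBC | D1, 7, 15, 22 = 4 | D1, 7, 15, 22 = 4 | D1 = 1 |
| Chemistry/LFT | D1, 7, 15, 22 = 4 | D1 = 1 | D1 = 1 |
| Coagulation | D7, 15, 22 = 3 | D1 = 1 | D1 = 1 |

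After Day 1, in the order CBC / chemistry / coagulation:
- Arm B Cycle 1: 3 / 3 / 3
- C2 start: 3 / 0 / 0
- C3 or later: 0 / 0 / 0

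**Step 3: does the pre-treatment draw change this?** Adding the crossover visit gives 2 / 2 / 2 for C3 or later. Adding the screening draw gives 5 / 5 / 4 for Arm B. Footnote 7 lets Arm B omit the Day 1 CBC and chemistry repeat when screening was within 3 days. None of this alters the after-Day-1 counts, which are the ones that can show toxicity of the combination.

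**Step 4: longest gap between scheduled CBC or chemistry tests.**
- C3 or later: Day 1 to the next Day 1 = 28 days. With the ±3-day window at both ends, the maximum is 28 + 3 + 3 = 34 days.
- Arm B Cycle 1: intervals are 7 − 1 = 6, 15 − 7 = 8, 22 − 15 = 7 and 29 − 22 = 7, so the longest is 8 days. With windows (±1 day in the first 4 weeks, ±3 after), the longest is Day 21 to Day 32 = 11 days.

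**Step 5: against Section 4.11.1.** Its wording gives no starting point. If its four weeks run from first combination dosing, the schedule in Step 2 does not deliver them. If they run from study entry, a subject starting azacitidine on Day 57 has finished the weekly tests about four weeks before the drug they are listed against is given.

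**The case against.** **Section 4.11.1 is not breached.** A reader might infer that the protocol contradicts its own risk table. It does not, strictly. The GSK2879552 row of the same table uses the same weekly-then-monthly wording, and Section 7 uses the same period for early study visits. Read as one common schedule counted from first study treatment, the tables comply. This stands, and the point is about adequacy rather than contradiction.

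**The subject may restart at Arm B Cycle 1.** Section 4.6 speaks of crossing to Arm B with a new baseline, and the Arm B tables attach a crossover footnote to the screening marrow cell: "Subjects who progressed to AML and cross over to Arm B will be required to have bone marrow for disease assessment". That could suggest entering the Arm B table at its first column. But the footnote requires only a marrow before combination dosing and concerns subjects with AML, while the instruction to go on with the next monotherapy visit points the other way. Some ambiguity remains, and a safety schedule should not rest on it.

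**Other safeguards exist.** Section 7.3 permits added tests but schedules none. Section 7.3.9 requires significantly abnormal results to be repeated, but an abnormality must first be seen. Medical-monitor approval and the crossover-visit bloods precede azacitidine. Prior hypomethylating treatment is an entry criterion for everyone, yet Arm B subjects with the same history still get weekly tests. The hepatic and renal risks in Section 4.11.1 are described mainly for severe pre-existing impairment or other chemotherapy combinations, so the chemistry gap weighs less than the CBC gap.

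**The nadir rule.** A reader might also infer that dose adjustment on nadir counts (Section 5.5.3) fails specifically for crossover subjects. Day-1-only CBC from Cycle 3 applies to everyone. What is particular to crossover is the lack of weekly tests in the first combination cycle.

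**Conclusion.** The point holds as a gap in the schedule on the natural reading of Section 4.6 and footnote 14. In a first combination cycle at Cycle 3 or later there are 0 scheduled tests per panel after Day 1, against 3 per panel in Arm B Cycle 1, and the longest nominal interval is 28 days against 8. At a Cycle 2 start, only chemistry/LFT and coagulation are affected.

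This assumes continued cycle numbering, which the text favors but does not state outright. How many subjects are affected cannot be derived: the protocol gives no crossover rate or timing. The planned Arm A total of 6 + 28 = 34 should not be read as a ceiling, because Section 4.8 allows about 3 to 12 subjects in Part 1 of each arm, plus replacements and further cohorts. Nor are crossover subjects left without any testing: they have the crossover visit and Day 1 of each cycle. This is a cheap, worthwhile improvement to patient safety.

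**What to change.** State in Section 4.6, and by a footnote in the Section 7.1 tables, that the first combination cycle after crossover has CBC, chemistry/LFT and coagulation on Days 1, 7, 15 and 22, whatever its cycle number, with Day 9 replacing Day 7 on the 5+2 azacitidine schedule. Name Day 1 explicitly for coagulation: simply copying Arm B Cycle 1, which has no Day 1 coagulation draw, would remove the one the present schedule gives.

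The cost is amendment wording and routine bloods. For a start at Cycle 3 or later, the Arm B office-visit row already covers the azacitidine days ("15 and 22 C3 and after: D1-7"), so only Days 15 and 22 are new: about two short visits per crossover subject. A Cycle 2 start needs no extra visit, only added chemistry and coagulation draws at visits already planned.
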